---

## 1 STUDY SYNOPSIS

Study Title	Transcatheter Aortic Valve Implantation with or without on-site Cardiac Surgery: the TRACS trial
Protocol version	V2
Date	February 20, 2024
Study Sponsors	
Azienda USL di Bologna, Bologna, Italy
 
Azienda Ospedaliero Universitaria di Ferrara, Cona (FE), Italy
 
Azienda USL-IRCCS di Reggio Emilia, Reggio Emilia, Italy
 
The present trial received the endorsement of the Italian Health Minister that partially supported the conduction of the study with the grant GR-2021-12374295 (Ricerca Finalizzata 2021)

Study Principal Investigator	[name]
Study Chairs	
[name]
 
[name]

Study Objectives	
The primary efficacy objective is to determine whether a TAVI pathway based on experienced operators who perform the procedure in the center without on-site cardiac surgery is non inferior compared to the one with the same team who perform the procedure in the center with on-site cardiac surgery in terms of all-cause death, stroke and rehospitalization for cardiovascular cause..
 
The primary safety objective is to demonstrate that mortality associated with periprocedural complications actionable by emergent cardiac surgery did not differ between study arms.

Study design	
TRACS is an all-comer, prospective, randomized, multicenter, open-label trial with blinded adjudicated evaluation of outcomes (PROBE). The TRACS trial will involve centers without on-site cardiac surgery, but with experienced operators already performing TAVI at the referring center with on-site cardiac surgery. Thus, participating centers and their study TAVI operators must follow selective criteria for eligibility. Participants will be recruited after Heart Team indication to TAVI procedure. The eligibility of each single patient to the study MUST BE CONFIRMED and VALIDATED by unanimous decision of the Heart Team. Study patients will be randomized in a 2:1 fashion to TAVI procedure performed by the same experienced operators either in the center without on-site cardiac surgery or in the referring center with on-site cardiac surgery.

Study arms	
EXPERIMENTAL ARM: TAVI WITHOUT ON-SITE SURGERY
 
After randomization, study TAVI operators of the participating center will schedule

	
the patient for TAVI in their hospital without on-site surgery.
 
CONTROL ARM: TAVI WITH ON-SITE SURGERY
 
After randomization, the patient will immediately be placed on the waiting list of the referring center with on-site cardiac surgery. Study TAVI operators of the participating center will perform the TAVI procedure in the hospital with on-site surgery according to the waiting list schedule of the latter.

Number of participants	566
Trial Location	Approximately 20 Italian centers without on-site cardiac surgery
Requirements for participating centers	
 
1. Availability of standard operating procedure with a cardiac surgery department for an established, weekly Heart Team discussion
 
2. Availability of standard operating procedure for the rapid transfer of patients with procedural complications to cardiac surgery with a maximum delay of 60 minutes (maximum distance between centers 90 km)
 
3. Five-year experience in screening, selection, and management of TAVI patients
 
4. At least 2 certified operators or a dedicated intercenter team performing the TAVI procedure (see detailed criteria list)
 
5. At least 3-year experience in performing TAVI procedures in a center with on-site cardiac surgery, with participation (as equipe) in at least 100 TAVI procedures
 
6. At least 5-year experience in advanced cardiac imaging including transoesophageal echocardiography and cardiac computed tomography
 
7. On-site vascular surgery or on-site availability of certified surgeon and operating room allowing the surgical treatment of vascular complications
 
8. On-site electrophysiology laboratory (permanent pacemaker implantation)
 

Requirements for study TAVI operators	
 
1. At least 5-year experience in coronary interventions
 
2. More than 75 PCIs per year
 
3. Experience in the use of tools for retrieval of intravascular foreign bodies
 
4. Experience in pericardiocentesis
 
5. Experience with ultrasound-guided puncture of the femoral artery
 
6. Experience in suture-mediated closure of femoral artery access
 
7. Experience in the management of peripheral vascular complications
 
8. At least 2-years experience in TAVI procedures as first and second operator
 
9. At least 50 TAVI procedures as first operator
 
10. More than 20 TAVI by year
 

Inclusion criteria	
 
1. Severe aortic stenosis
 
2. Indication to TAVI confirmed by the Study Heart Team
 
 
AND one of the following:
 
 
1. Inoperable due to prohibitive operative risk
 
2. High surgical risk as defined as STS score >8%
 

	
3. The presence of at least one clinical factor that, by unanimous judgment of the Study Heart Team, compromises the benefit/risk ratio in the case of emergent cardiac surgery:
 
 
• Porcelain aorta or severely atherosclerotic aorta
 
• Frailty/Reduced physical performance
 
• Cognitive impairment, dementia, or Parkinson's disease
 
• Severe liver disease/cirrhosis
 
• Hostile chest
 
• Internal mammalian artery or other critical conduit(s) crossing midline and/or adhering to the posterior table of the sternum
 
• Severe pulmonary hypertension and/or severe right ventricular dysfunction
 
• Severe Chronic Obstructive Pulmonary Disease (COPD)
 
• Age <math>\geq</math>85 years
 
 
It is mandatory for the inclusion in the study that the Study Heart Team confirm by unanimous judgment the eligibility of each single patient. It is in charge of the Study Heart Team to weight the feasibility and to estimate the eventual efficacy of emergent cardiac surgery and based on this assessment to proceed or not with the eligibility. If the Study Heart estimates the emergent cardiac surgery feasible and potentially effective, the patient cannot be considered eligible.


Exclusion criteria
	
 
1. Unsuitable for transfemoral TAVI
 
2. Emergent TAVI
 
3. Noncardiovascular comorbidity reducing life expectancy to <1 year
 
4. Any factor precluding 1-year follow-up
 
5. Refusal informed consent
 

Primary endpoint
	
One-year cumulative occurrence of all-cause death, stroke and hospital readmission for cardiovascular causes
 
The adverse events will be collected from the time of randomization, also considering adverse events during the waiting time for the TAVI procedure.

Secondary efficacy endpoints
	
 
• All-cause death
 
• Cardiovascular death
 
• Myocardial infarction
 
• Hospital admission for cardiovascular cause
 
• Hospital admission for heart failure
 
• Cerebrovascular accident
 
• Ischemic stroke
 

	
 
• Hospital admission for pneumonia (<math>\pm</math> respiratory failure)
 
• Need for balloon aortic valvuloplasty for emergent condition
 
• Quality of life measured with the Eq-5D and KCCQ-12 scales
 
• Time spent on the waiting list before TAVI
 

Primary safety endpoint	Death due to periprocedural complications that can be addressed with emergent cardiac surgery
Other safety endpoints	
 
• Cardiac tamponade
 
• Bleeding
 
• Kidney failure (requirement of renal replacement therapy)
 
• Severe aortic regurgitation (aortic regurgitation according to current guidelines)
 
• Multiorgan failure (failure of at least two organ systems)
 
• Vascular access site and access related complications
 
• Conduction disturbances and arrhythmias
 
• Endocarditis
 
• Valve thrombosis
 
• Valve malpositioning
 
• Valve embolization
 
• Ectopic valve deployment
 
• TAV-in-TAV deployment
 

Assessment Schedule	Pre-eligibility screening, inclusion, randomization, TAVI, 1-month visit after TAVI, 6-month visit after TAVI, 12-month visit after TAVI, and every 12 months thereafter.
Study Duration	Enrollment will occur over approximately 2 years with an expected minimum follow-up of 12 months. All patients will be followed until 3 years.
Clinical Event Adjudication Committee	A blinded Clinical Event Adjudication Committee will adjudicate adverse events.
Data and Safety Monitoring Board	An independent Data and Safety Monitoring Board will advise the Steering Committee on the safety aspects and overall progress of the study.
Statistical Considerations	The estimated rate of the primary endpoint is around 30%, considering the characteristics of the study population and the inclusion of adverse events before TAVI [1-29]. Overall, 560 (187 control arm and 373 experimental arm) patients are required to exclude a difference in favor of the control group of more than 10% ( $\alpha=5\%$ and $\beta=20\%$ ). Considering a 1% attrition rate final sample size is inflated to 566 patients.

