## 2.6 The balance between the burden of the waiting list and saved lives from ECS

As stated above, TAVI procedure may cause lethal complications that ECS may save in half of the cases. However, it should be considered that the same patients carry a significant risk of events while waiting for TAVI in the center with on-site CS if such wait is longer than 2-3 months. To date, no study has investigated the balance between the two burdens, but available data could support an estimate.

If we supposed to have 1000 patients with indication to TAVI, 10 of them are expected to need ECS during TAVI procedure. Based on the literature, ECS will save the life of 5 (50%) patients, mainly the youngest, with few comorbidities and less complex complications. On the contrary, we could expect that in a center without on-site CS all 10 patients would die. The absolute risk reduction (AAR) in the center with on-site CS is 0,005 with a **number needed to treat (NNT) equal to 200 patients**.

On the other hand, according to the literature, in patients waiting at least 3 months for TAVI in a center with on-site CS, we could expect a mortality of around 4% during this wait. If extending TAVI of inoperable or high surgical risk to centers without on-site CS reduces the time spent on the waiting list by the 50%, we could expect that even mortality could be reduced to 2%. The absolute risk reduction of halving the waiting time for TAVI could be 0,02 with a **number needed to treat equal to 50 patients**.

Although this hypothesis should be taken with caution, the different weight of these NNTs should be considered.

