### 4.3 Primary safety endpoint

- Death due to periprocedural complications actionable by emergent cardiac surgery

To test whether mortality due to periprocedural complications actionable by emergent cardiac surgery differs between the TAVI procedures performed in the center without on-site cardiac surgery and the TAVI procedures performed by the same team in the center with on-site cardiac surgery.

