## 6 STUDY POPULATION

### 6.1 Inclusion criteria

3. Severe aortic stenosis
4. Indication to TAVI confirmed by the Study Heart Team

AND one of the following:

4. Inoperable due to prohibitive operative risk \*
5. High surgical risk as defined as STS score >8% \*
6. The presence of at least one clinical factor compromising the benefit/risk ratio in the case of emergent cardiac surgery \*:

- Porcelain aorta or severely atherosclerotic aorta
- Frailty/Reduced physical performance
- Cognitive impairment, dementia, or Parkinson's disease
- Severe liver disease/cirrhosis
- Hostile chest
- Internal mammalian artery or other critical conduit(s) crossing midline and/or adhering to the posterior table of the sternum
- Severe pulmonary hypertension and/or severe right ventricular dysfunction
- Age ≥85 years
- Severe Chronic Obstructive Pulmonary Disease (COPD)

**\*: It is mandatory for the inclusion in the study that the Study Heart Team confirm by unanimous judgment the eligibility of each single patient. As described below, it is in charge of the Study Heart Team to weight the feasibility and eventual efficacy of emergent cardiac surgery and based on this assessment to proceed with the eligibility. If the Study Heart estimates the emergent cardiac surgery feasible and potentially effective, the patient cannot be considered eligible.**

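### The primary safety objective promises to demonstrate that mortality did not differ, but the plan only tests for a difference, sets no margin, and expects about five deaths

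*Protocol*

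**What the plan says.** The protocol describes the primary safety comparison in two places, in different terms.

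- Synopsis, Study Objectives: "The primary safety objective is to demonstrate that mortality associated with periprocedural complications actionable by emergent cardiac surgery did not differ between study arms".
- Section 4.3: "To test whether mortality due to periprocedural complications actionable by emergent cardiac surgery differs between the TAVI procedures performed" in the two kinds of center.

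The first promises a conclusion of no difference. The second describes an ordinary test of difference. The one sample-size calculation (Synopsis and Section 9.1) rests on a primary efficacy rate of around 30% and a 10-point margin. It yields 187 control and 373 experimental patients, 560 in all, inflated to 566. No margin, assumed rate or power is attached to the safety endpoint. Section 9 names the chi-square test for categorical variables, with significance at 0.05.

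Section 2.6 is the only place that puts rates for this kind of death side by side: "If we supposed to have 1000 patients with indication to TAVI, 10 of them are expected to need ECS during TAVI procedure"; with on-site surgery, "ECS will save the life of 5 (50%) patients"; without it, "we could expect that in a center without on-site CS all 10 patients would die". The same section asks that the hypothesis be taken with caution.

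**The concern.** A test that fails to reject equality shows equality only if it would very probably have rejected a difference that matters. The protocol respects this for efficacy, where it sets a non-inferiority objective and a margin. It does not do so for safety, although this endpoint isolates the specific risk of working without a surgical department on site. If deaths are as rare as Section 2.6 suggests, the test will almost always be non-significant, including when mortality in the experimental arm is double that in the control arm. A primary objective worded as demonstrating no difference then invites a reassuring statement that the data cannot carry, on the question that decides whether TAVI can move to centers without cardiac surgery.

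**Working it through.** **Inputs.** Arm sizes are 187 and 373 (Synopsis, Section 9.1). Of 1000 patients, 10 need emergent surgery; 5 of them die with on-site surgery and 10 without (Section 2.6). The test is chi-square at two-sided 0.05 (Section 9; two-sided is an assumption here). Fisher's test is shown alongside because the counts are small.

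**The protocol's own figure.** Section 2.6 gives an absolute difference of 10/1000 - 5/1000 = 0.005 and a number needed to treat of 1/0.005 = 200. Both reproduce. There is no stated figure for the safety endpoint's power or event count.

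**Expected deaths** (n × rate):
- Control: 187 × 0.005 = 0.94
- Experimental: 373 × 0.010 = 3.73
- Chance of no control death: 0.995^187 = 0.39

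**Power.** This is the sum, over all pairs of counts (c, e), of Bin(c; 187, pC) × Bin(e; 373, pE) wherever the test gives p ≤ 0.05.

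| Control | Experimental | Expected deaths | Chi-square | Fisher |
|---|---|---|---|---|
| 0.5% | 1.0% | 0.9 / 3.7 | 2.2% | 0.9% |
| 0.75% | 1.0% | 1.4 / 3.7 | 2.6% | 1.5% |
| 0.8% | 1.0% | 1.5 / 3.7 | 2.8% | 1.7% |
| 1.0% | 2.0% | 1.9 / 7.5 | 9.7% | 6.5% |
| 0.5% | 2.0% | 0.9 / 7.5 | 21% | 15% |
| 0.5% | 3.0% | 0.9 / 11.2 | 52% | 45% |
| 0.5% | 4.5% | 0.9 / 16.8 | 85% | 82% |

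The 0.75% and 0.8% rows allow for later deaths. Section 8.15 sets no time limit on the death, and Section 3 puts mortality after emergent surgery near 80% at one year, so 1% × 0.8 = 0.8%. The 1% versus 2% row borrows the 2% ceiling on complications in Section 7.8 as an upper mortality scenario. That is an assumption, not a rate the protocol gives for deaths.

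**Patients needed for 80% power at 0.5% versus 1.0%, 2:1.** The pooled rate is (0.005 + 2 × 0.010)/3 = 0.00833. Control n = [1.96 × √(1.5 × 0.00833 × 0.99167) + 0.842 × √(0.005 × 0.995 + 0.010 × 0.990/2)]² / 0.005² ≈ (0.2182 + 0.0838)² / 0.000025 ≈ 3,650. The total is 3 × 3,650 = 10,950.

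**Precision at the expected result, 4/373 versus 1/187.** The difference is 1.07% - 0.53% = 0.54 points. The Wilson limits are 0.42% to 2.72% (experimental) and 0.09% to 2.97% (control). The Newcombe limits are:
- Lower: 0.54 - √((1.07 - 0.42)² + (2.97 - 0.53)²) ≈ -2.0 points
- Upper: 0.54 + √((2.72 - 1.07)² + (0.53 - 0.09)²) ≈ +2.2 points

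Fisher's p is 0.67. The upper limit is more than four times the 0.5-point difference in Section 2.6.

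**The case against.** **The rates are illustrative.** Section 2.6 concerns TAVI patients in general. The lives saved by surgery there are mainly those of younger patients with few comorbidities, whereas this trial's rule is: "If the Study Heart estimates the emergent cardiac surgery feasible and potentially effective, the patient cannot be considered eligible". Centers also need a rapid-transfer procedure (Section 8.1), so the assumption that every such patient dies is a worst case. This stands: a reader might infer that the protocol predicts a doubling among its own patients, and it does not. But the rates only set a scale. If surgery helps enrolled controls less, the control rate rises, the true difference shrinks, and power stays at about 3% or less (0.75% to 0.8% versus 1.0%).

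**Some harm would be detected.** This also stands. A reader might infer that the test must be non-significant whatever the harm; at 4.5% versus 0.5% it would reject at least 82% of the time. That harm is far above any rate the protocol mentions for these deaths.

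**No rule turns a non-significant result into proof of safety.** Correct. Section 4.3 is neutral, Section 9 provides for 95% confidence intervals where appropriate, and a separate analysis plan may say more. A reader might infer a formal decision rule, but none is written. The defect is the objective itself, which is fixed in the protocol and which an analysis plan cannot make attainable.

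**Safety is watched elsewhere.** The DSMB hears at once of each complication requiring emergent surgery and applies a 2% ceiling (Section 7.8), and deaths within a year count in the primary composite. Neither supplies the missing inference. The ceiling concerns complications and is not a between-arm comparison of deaths. The composite's 10-point margin is 20 times 0.5 points.

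**Population.** A reader might add that the conclusion must be restricted to patients unsuited to emergent surgery. That is no error in the plan: the Synopsis and Sections 3 and 6.1 already define that population.

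**Conclusion.** The objective cannot be met as written. With about 0.9 and 3.7 expected deaths, a doubling would go undetected about 98% of the time with the named chi-square test (99% with Fisher's), and the likely interval spans about two points either side of zero. A non-significant result would therefore not demonstrate that mortality did not differ.

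The size of the problem rests on the illustrative rates of Section 2.6 and a two-sided 0.05 level, but the conclusion holds across the plausible range: power is between about 2% and 21% by chi-square for experimental mortality of 1% to 2% against control mortality of 0.5% to 1% in the scenarios above. It does not extend to saying that no harm of any size could be found, or that the protocol contains a rule equating non-significance with safety. The efficacy analysis and its sample size are unaffected.

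**What to change.** Use the same wording in the Synopsis and Section 4.3, for example:

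> The primary safety objective is to estimate the between-arm difference in mortality due to periprocedural complications actionable by emergent cardiac surgery, with an exact or Newcombe 95% confidence interval, as a descriptive safety comparison. With the planned arms the interval is expected to extend about 2 percentage points either side of the estimate. A non-significant result will not be reported as showing no difference.

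This needs no extra patients, data or change of conduct. Its cost is that the sponsor gives up a claim the trial cannot support. Keeping a confirmatory safety claim would instead require a justified margin and a sample size for it; detecting the doubling alone would take about 10,950 patients.

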## 2 BACKGROUND

### 2.1 Indication to the TAVI procedure and the role of the Heart Team

Transcatheter aortic valve implantation (TAVI) has become standard therapy for elderly patients with symptomatic aortic stenosis. The PARTNER trials, CoreValve US High Risk, SURTAVI and Evolut Low risk studies were pivotal in presenting robust evidence for the safety, feasibility, and efficacy of TAVI with both self- and balloon-expandable prostheses in the management of aortic stenosis in patients from high to low surgical risk and paved the way for clinical use worldwide [1-7]. Accordingly, valvular heart disease (VHD) guidelines suggested TAVI as a valid option for all patients aged 75 years or more, when decisions concerning treatment and intervention derive from an active and collaborative Heart Team with expertise in VHD. The Heart Team is a group of qualified healthcare professionals comprising clinical and interventional cardiologists, cardiac surgeons, interventional imaging specialists, cardiovascular anesthesiologists, and other specialists if necessary (e.g., heart failure specialists or electrophysiologists, geriatrics). The role of the Heart Team is crucial, since it can comprehensively discuss the accuracy of surgical risk scores, consider the additional role of unaccounted comorbidities or frailty, and perform a risk-benefit analysis that includes other factors not necessarily caught in standard procedures or protocols. Therefore, Heart Teams play a crucial role in decision making and the European Society of Cardiology strongly supports its consultation for the treatment of VHD [8].

### 2.2 Heart Valve Centers and TAVI in centers with on-site cardiac surgery

The VHD guidelines support Heart Valve Centers as centers of excellence in the treatment of VHD to provide optimal quality of care with a patient-centered approach. This is achieved through high procedural volume in conjunction with specialized training, continuous education, and focused clinical interest. The main requirements of a Heart Valve Centre are on-site institutional cardiology and cardiac surgery (CS) departments, an active and collaborative Heart Team, and the institution of a Heart Valve Clinic (Table 1). The latter consists of a structured and dedicated outpatient clinic where the cardiologist in charge should have competencies in treating patients with VHD. Recent evidence shows that access to these Heart Valve clinics improves outcomes in patients with aortic valve stenosis. Beside the whole spectrum of valvular interventions, expertise in interventional and surgical management of coronary artery disease (CAD), vascular diseases, and complications must be available [8].

Requirements
Centre performing heart valve procedures with institutional cardiology and cardiac surgery departments with 24 h/7-day services.
Heart Team: clinical cardiologist, interventional cardiologist, cardiac surgeon, imaging specialist with expertise in interventional imaging, cardiovascular anaesthesiologist.
Additional specialists if required: heart failure specialist, electrophysiologist, geriatrician and other specialists (intensive care, vascular surgery, infectious disease, neurology). Dedicated nursing personnel is an important asset to the Heart Team.
The Heart Team must meet on a frequent basis and work with standard operating procedures and clinical governance arrangements defined locally.
A hybrid catheterization laboratory is desirable.
The entire spectrum of surgical and transcatheter valve procedures should be available.
High volume for hospital and individual operators.
Multimodality imaging including echocardiography, CCT, CMR, and nuclear medicine, as well as expertise on guidance of surgical and interventional procedures.
Heart Valve Clinic for outpatient and follow-up management.
Data review: continuous evaluation of outcomes with quality review and/or local/external audit.
Education programmes targeting patient primary care, operator, diagnostic and interventional imager training and referring cardiologist.

© ESC/EACTS 2021

CCT = cardiac computed tomography; CMR = cardiac magnetic resonance.

Table 1: Requirements for a Heart Valve Center according to the ESC 2021 VHD Guidelines.

